8.3 Database management and quality control

Novartis staff review the data entered into the CRFs by investigational staff for completeness and accuracy and instruct the site personnel to make any required corrections or additions.

Queries are sent to the investigational site using an electronic data query. Designated investigator site staff is required to respond to the query and confirm or correct the data. If the electronic query system is not used, a paper Data Query Form will be faxed to the site. Site personnel will complete and sign the faxed copy and fax it back to Novartis staff that will make the correction to the database. The signed copy of the Data Query Form is kept at the investigator site.

Concomitant medications entered into the database will be coded using the WHO Drug Reference List, which employs the Anatomical Therapeutic Chemical classification system. Concomitant procedures, non-drug therapies and adverse events will be coded using the Medical dictionary for regulatory activities (MedDRA) terminology.

Laboratory samples will be processed centrally and the results will be sent electronically to Novartis.

Randomization codes and data about all study drug(s) dispensed to the patient and all dosage changes will be tracked using an Interactive Response Technology (IRT). The system will be supplied by a vendor, who will also manage the database. The database will be sent electronically to Novartis.

Each occurrence of a code break via IRT will be reported to the clinical team and monitor. The code break functionality will remain available until study shut down or upon request of Novartis.

The occurrence of relevant protocol deviations will be determined. After these actions have been completed and the database has been declared to be complete and accurate, it will be locked. The core and OLE data will be locked separately for each analysis, according to Data Management Plan. The treatment codes will be unblinded and made available at the core part database lock. Any changes to the database after each database lock can only be made after written agreement by Novartis Development management.

8.4 Data Monitoring Committee

An external data monitoring committee (DMC) independent of Novartis will be appointed to monitor the study conduct and to determine if it is safe to continue the study according to the protocol. If applicable, the recommendation may include any new relevant safety issue(s) identified by the DMC during the evaluation.

The membership of the DMC and the responsibilities of the DMC and Novartis will be defined in a separate document entitled the "Data Monitoring Committee Charter." The DMC Charter will include information about data flow, purpose and timing of DMC meetings, guidance in the decision making process, communication strategy, procedures for ensuring confidentiality, procedures to address conflicts of interest and statistical monitoring guidelines.

The DMC will only cover the core part.

8.5 Adjudication Committee

8.5.1 Clinical Endpoint Committee

All events, which could potentially fulfill the criteria for the primary or secondary endpoints will be assessed during the core part and reported to the Clinical Endpoint Committee (CEC) for adjudication.

The CEC will be responsible for classifying all death events and for determining whether pre-specified endpoint criteria were met for the non-fatal events. Sites are instructed to take a conservative approach when reporting endpoints; if the investigator suspects an endpoint may have occurred, it should report the event to the CEC for the final determination. The membership and responsibilities of the CEC Committee will be defined in a separate document provided to the sites. This document will include definitions for endpoints and guidelines on the endpoint reporting process.

No adjudication of clinical endpoint events during the OLE epoch will take place.

8.5.2 Angioedema Adjudication Committee

If an angioedema or angioedema-like event occurs, the investigator will complete an Adjudication Questionnaire for an Angioedema-like Event form (provided by Novartis). Details on the process of reporting angioedema and angioedema-like events are outlined in a manual provided to investigators.

Submission of an angioedema report is not a substitution for the submission of an SAE report. If an angioedema-like event satisfies the definition of an SAE, the investigator must submit an SAE report in addition to the Adjudication Questionnaire for an Angioedema-like Event.

All angioedema reports will be forwarded to an angioedema adjudication committee by Novartis for assessment. The membership and responsibilities of the Angioedema Adjudication Committee are defined in a separate document that will be provided to the sites.

The process above will also be applied to the OLE epoch.

9 Data analysis

9.1 Analysis sets

The following populations will be used for the core part statistical analyses:

The Screened Set (SCR) will consist of all patients who signed the informed consent. The screened set includes only unique screened patients, i.e., in the case of re-screened patients only the chronologically last screening data is counted.

The Enrolled Set (ENR) (run-in epoch) will consist of all patients who received at least one dose of run-in study medication.

The Randomized Set (RAN) will consist of all patients who received a randomization number, regardless of receiving double-blind investigational drug.

The Full Analysis Set (FAS) will consist of all randomized patients with the exception for those patients who have not been qualified for randomization and have not received investigational drug, but have been inadvertently randomized into the study. Following the intent-to-treat principle, patients will be analyzed according to the treatment to which they were assigned at randomization. Efficacy variables will be analyzed based on the FAS as the primary population.

The Safety Population (SAF) will consist of all randomized patients who received at least one dose of double-blind medication. Patients will be analyzed according to the treatment actually received. The safety population will be used for the analyses of safety variables.

The Per-protocol (PP) population will be a subset of the FAS which will consist of the patients who do not have major deviations from the protocol procedures in the double-blind study stage. Major protocol deviations will be pre-specified prior to un-blinding treatment codes for analyses. This supplemental efficacy population will be used to support the primary analysis results.

The following populations will be used for the OLE statistical analyses:

The Extension Population (EXT): All eligible patients who have completed the core part and have signed the informed consent for the OLE epoch.

The Full Analysis Set for OLE epoch (FAS-Ext): All patients who receive at least one dose of the extension study drug. The FAS-Ext population is the analysis set for both safety and efficacy analysis.

9.2 Patient demographics and other baseline characteristics

In the core part, baseline value is defined as the last non-missing assessment prior to the first dose of randomized study medication unless specified otherwise.

In the OLE epoch, value at Visit 301 is defined as OLE baseline.

Summary statistics will be provided by treatment group for demographics and baseline characteristics, including age, age group (< 65 years vs. \geq 65 years; < 75 years vs. \geq 75 years), sex, race, ethnicity, weight, height, body mass index (BMI), category of prior CHF

medication, prior HF hospitalization, NYHA class, LVEF, NT-proBNP, eGFR, and vital signs. BMI will be calculated as weight (kg)/height² (m²) from the collected height and weight at Visit 1 (Screening Visit). Continuous variables will be summarized using n, mean, standard deviation, median, minimum, and maximum. Categorical variables will be summarized using frequency and percentage.

The difference between treatment groups will be compared using the Chi-square test for categorical variables or using t-test for continuous variables. The p-values will be provided for descriptive purposes and will not be considered to define any formal basis for determining factors to be included in statistical models. If a substantial imbalance of treatment groups with respect to some variables does occur, supplemental analyses with addition of these variables in model may be performed to assess the potential impact on efficacy as appropriate.

The FAS will be the patient population for the above analyses.

Similarly, summary statistics as given above will be presented in the OLE epoch.

9.3 Treatments

The overall duration on the double-blind investigational treatment will be summarized by treatment group using mean, standard deviation, median, minimum, and maximum. Additionally, the number and percentage of patients will be summarized by treatment group for duration category. Mean doses and dose levels will be summarized by treatment group and visit. The overall duration on the investigational product in the OLE epoch will be analyzed similarly.

Concomitant medications and significant non-drug therapies, prior to and after the randomization date respectively, will be summarized by therapeutic class, preferred term, and treatment group for the safety population. Concomitant therapies used during the single-blind run-in epoch will also be similarly summarized. Concomitant medications in the OLE epoch will also be similarly summarized.

The number and percentage of patients on different CHF background medications (e.g., mineralocorticoid receptor antagonist, β -blockers, diuretics, digoxin) will be tabulated by treatment at baseline and during the double-blind stage. Similarly, the number and percentage of patients on different CHF background medications will be tabulated in the OLE epoch.

9.4 Analysis of the primary variable

9.4.1 Variable

The primary efficacy variable is time to the first occurrence of the composite endpoint, which is defined as either CV death or HF hospitalization. The confirmation of the primary composite events is based on an adjudication process by independent CEC ([Section 8.5.1](#)).

9.4.2 Statistical model, hypothesis, and method of analysis

The primary efficacy variable will be analyzed using Cox proportional hazards model with treatment and the stratification factor of screening NT-proBNP ($< 1,600$ pg/mL, $\geq 1,600$ pg/mL) as fixed-effect factors. The primary hypothesis to be tested is $H_{10}: \lambda_2/\lambda_1 \geq 1$ versus $H_{1a}: \lambda_2/\lambda_1 < 1$, where λ_1 and λ_2 are hazards for enalapril treatment and LCZ696

treatment, respectively. The frequency of patients with composite primary endpoint events and the treatment exposure adjusted event rate will be provided for individual treatment arm.

The FAS will be used for the primary analysis.

The primary objective is met when the hazard ratio point estimate is less than 1.

9.4.3 Handling of missing values/censoring/discontinuations

The primary efficacy variable, the time to the first occurrence of either CV death or HF hospitalization, will be considered as censored for patients who have no event and at least one of the following applies:

- withdrawal of informed consent,
- loss to follow-up, or
- death from non-CV causes.

For those patients without events, the censoring date will be defined as the following (whichever occurs first):

- date when the patient withdrew informed consent,
- date of the patient's last visit,
- date of death from non-CV causes.

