3.1.1.3 Double-blinded randomized treatment epoch

The randomized treatment epoch will begin at Visit 201. Patients who successfully complete the run-in and tolerate LCZ696 50 mg b.i.d. will be randomized to receive LCZ696 100 mg b.i.d. or enalapril 5 mg b.i.d. for 4 weeks and be up-titrated to the target dose of LCZ696 200 mg b.i.d. or enalapril 10 mg b.i.d. in a 1:1 ratio in a double-blind manner. Please refer to [Table 6-1](#) for a detailed list of study procedures and assessment to be performed at each randomized treatment epoch visit.

The study medication will be added to the prescribed background HF therapy. Concomitant administration of ACEIs or ARBs with the study medication is strictly prohibited. Please refer to [Section 5.5.7](#) for more information on co-administration of other medications.

Reported trial outcome endpoint events will be collected as they occur throughout the randomized treatment epoch. All laboratory evaluations for planned visits after randomization

will be performed through the central laboratory or other authorized laboratory. Unscheduled laboratory assessments can be performed locally as necessary.

Visit 201 will be considered the reference visit for all study visits during the randomized treatment epoch. Regardless of the occurrence of any unscheduled visits, scheduled visits should occur within the timeframe in relation to Visit 201 as outlined in [Table 6-1](#).

Randomization Visit (Visit 201)

Patients who have met all the inclusion criteria and none of the exclusion criteria at the end of the active treatment run-in epoch will be randomized to either LCZ696 100 mg b.i.d. or enalapril 5 mg b.i.d. in a 1:1 ratio.

Site personnel should instruct the patient to refrain from taking their run-in medication on the day of Visit 201. Site personnel will document the date and time of the last dose of the LCZ696 run-in medication. This is necessary to ensure a 36-hour wash-out period to avoid overlapping of LCZ696 with enalapril and minimize the potential risk of occurrence of angioedema.

If appropriate, the patient will start to take the double-blind study medication (LCZ696 100 mg b.i.d. or enalapril 5 mg b.i.d.) the day after Visit 201. For example, if a patient's Visit 201 is on Wednesday, he/she must not take any doses of the LCZ696 50 mg b.i.d. run-in medication after Tuesday evening. The patient will then start taking the first dose of the double-blind study medication on Thursday morning.

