dose of the study drug to the lower dose level. The dose of background disease modifying drugs, such as β -blockers and aldosterone antagonists, may be modified to facilitate maintenance of study drug if they are believed to be the cause of the adverse effect in question. If the situation is not rectified despite adjusting/discontinuing other concomitant medications or if adjusting other concomitant medications is not possible, patients who no longer tolerate the intermediate or target doses at any time during the double-blind treatment epoch of the trial can be down-titrated to the lower dose level at the investigator's discretion (please refer to [Table 5-1](#) for dose levels available for titration). However, every attempt should be made to re-challenge the patients so that they are kept on the maximal tolerated dose of study drug for as long a duration as possible throughout the randomized treatment epoch of the trial. Please refer to [Section 5.5.5](#) for guidance on study drug dose adjustment.

If the study drug is temporarily discontinued, it should be reintroduced as soon as medically justified in the opinion of the investigator. After randomization, study drug discontinuation for any reason does not constitute withdrawal from the study and should not lead to the patient being withdrawn from the study. On the contrary, even patients who have stopped taking study drug are expected to attend all the protocol specified study visits and perform all measurements as stipulated in the visit schedule. In case it is not possible for the patient to attend any visit(s), the site staff will keep in touch with the patient by means of regular phone contact with the patient himself/herself or with the person pre-designated by the patient accordance with the patient's study visit schedule. Data will continue to be collected about the patient's health status, including information on developing of cardiovascular complications and vital status. This information may be provided by either the patient himself/herself or patient's designee. Data, such as information on survival information and potential protocol-specified endpoint, might be also collected from a health care provider, or other sources as available as allowed by local regulation or restriction. These data will be collected until the conclusion of the study, even if the patient is no longer attending the study visits in person.

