5.5.9 Discontinuation of study treatment

Patients may voluntarily discontinue study treatment for any reason at any time. The investigator should discontinue study treatment for a given patient if, on balance, he/she believes that continuation would be detrimental to the patient's well-being.

Study treatment discontinuation during the double-blind treatment epoch does not constitute withdrawal from the study, does not constitute withdrawal of consent and should not lead to the patient being withdrawn from the entire study unless the patient specifically withdraws his/her consent. Patients who have discontinued study drug are expected, and should be encouraged to, attend all the protocol specified study visits and perform all measurements as stipulated in the visit schedule ([Table 6-1](#)) and remain in follow up for the duration of the trial. If they fail to return for these assessments for unknown reasons, every effort (e.g., telephone, e-mail, letter) should be made to contact them as specified in [Section 5.5.11](#). The investigator must also contact the IRT to register the patient's discontinuation from study treatment.

During the OLE epoch, permanent discontinuation of LCZ696 constitutes withdrawal from the study. Under these circumstances, the patient should be evaluated at a final study visit (Visit 399). The investigator must also notify the IRT of the patient's discontinuation of LCZ696 and record it on the Drug Administration Record of the eCRF.

If the patient does not attend the study visits, follow-up should continue according to the specified schedule by telephone to determine if any AEs/endpoints pre-specified in the protocol have occurred, except in the case that the patient **specifically** refuses such follow-up and withdraws his/her consent.

The emergence of the following circumstances will require permanent investigational drug discontinuation:

- Withdrawal of informed consent
- Investigator thinks that continuation would be detrimental to the patient's well-being.
- Suspected occurrence of angioedema. A patient with any signs or symptoms of clinically significant angioedema should be thoroughly evaluated by the investigator.

The emergence of the following circumstances will require temporary or permanent discontinuation (study drug may be restarted once these circumstances no longer exist except the case of permanent discontinuation during the OLE epoch):

- Pregnancy and post-pregnancy during lactation period

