5.5.11 Loss to follow-up

For patients whose status is unclear because they fail to appear for study visits without stating an intention to withdraw, the investigator should show "due diligence" by contacting the patient, the patient's family, friends and family physician as agreed in the informed consent and by documenting in the source documents steps taken to contact the patient, e.g., dates of telephone calls, registered letters, etc. A patient should not be formally considered lost to follow-up until his/her scheduled end of study visit would have occurred.

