withdrawn from the study. Patients who discontinue study drug should be requested to return for all of the assessments outlined in [Table 6-1](#) as scheduled. If any patient refuses to return for these assessments or is unable to do so, every effort should be made to contact him/her or knowledgeable informant by telephone to ask if any of the study endpoint events have occurred at the foreseen visit dates for the remaining duration of the study. Documentation of attempts to contact the patient should be recorded in the source documentation.

At a minimum, patients who not participating in the OLE epoch will be contacted for safety evaluations during the 30 days following the last study visit or following the last administration of investigational treatment if there are post-treatment follow-up visits (whichever is later), including a final contact at the 30-day point. Documentation of attempts to contact the patient should be recorded in the source documentation.

Patients should be instructed NOT to eat or drink anything (except water) for approximately 8 hours prior to each scheduled fasting laboratory evaluation (see [Section 6.5.4](#)). If the patient has not fasted, the study visit collection of samples for laboratory evaluations should still take place.

Patients will be instructed to take the last dose of the double-blind study drug on the day before the core part EOS visit (Visit 299), and visit the study sites without taking the study drug on the day of Visit 299.

Patients will also be instructed to take study drug, as usual, on the morning of their site visits (except for Visit 201 and Visit 299), with or without food. If a patient did not take his/her study drug on the morning of his/her scheduled visit, the study visit could nevertheless be conducted. The only exception to this rule is for visits when the pre-study drug dose blood and urine samples for biomarker [REDACTED] are collected. In this case, the patient should not take the study drug before attending the study visit, but the study visit should be scheduled so that the biomarker [REDACTED] are obtained immediately before the time when the patient usually takes his/her study medication.

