9.4.4 Supportive analyses

In addition to the primary analysis, the primary efficacy variable will also be analyzed using the same primary analysis model in the PP population as supportive.

A supplemental log-rank test will be performed for both the FAS and the PP population. Survival function for each treatment group will be estimated by Kaplan-Meier method and the Kaplan-Meier curves will be presented for both the FAS and the PP populations.

The frequency and percentage of patients who reach the primary composite endpoint will be provided by treatment group for both the FAS and the PP population.

Additionally, similar analyses will be performed for each of the components of the composite endpoint with all events for that component that occurred during the double-blind treatment epoch of the study to quantify the strength of the effect for each component in the primary composite endpoint.

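### Event-free patients are censored at their last visit although endpoints are still collected remotely afterwards, so later follow-up counts only if it ends in an event

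*Protocol*

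**What the plan says.** Section 9.4.3 of the protocol sets the rule for the primary variable: "For those patients without events, the censoring date will be defined as the following (whichever occurs first"). The three dates are consent withdrawal, "date of the patient's last visit" and death from non-CV causes. A last-contact or last-known-event-free date is not among them.

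Other sections keep collecting endpoints after visits stop:

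- Section 3.1.1.3 takes health status and endpoint information from the patient, a designee or a health-care provider: "These data will be collected until the conclusion of the study, even if the patient is no longer attending the study visits in person".
- Section 5.5.9, for patients who do not attend visits: "follow-up should continue according to the specified schedule by telephone to determine if any AEs/endpoints pre-specified in the protocol have occurred".
- Section 6 (core part), for patients who refuse or are unable to return: "every effort should be made to contact him/her or knowledgeable informant by telephone to ask if any of the study endpoint events have occurred".
- Section 5.5.11: "A patient should not be formally considered lost to follow-up until his/her scheduled end of study visit would have occurred".

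On which events count, Section 3.1.1.3 says "Reported trial outcome endpoint events will be collected as they occur throughout the randomized treatment epoch", and Section 9.4.4 bases the component analyses on "all events for that component that occurred during the double-blind treatment epoch of the study". Section 9.4.2 analyses the full analysis set and declares the primary objective met if the hazard ratio point estimate is below 1.

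**The concern.** For a patient followed only remotely, the end of follow-up depends on the outcome. If a primary event is found by telephone after the last visit, it enters the Cox model at its own date, and all the time up to it counts as time at risk. If the same calls show no event, the time after the last visit is discarded. Censoring is then informative by construction, even if stopping visits has nothing to do with risk.

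The effect is to shrink the denominator. Kaplan-Meier curves, and any rate computed on this follow-up time, are too high in both arms. The hazard ratio is disturbed only if the arms differ in how many patients are followed this way, and the arm with more of them looks worse.

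The criterion has no margin to absorb this. Success is a bare point estimate below 1, and the planned 57 events give exactly the targeted 80% probability of it.

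**Working it through.** **The plan's own figure.** Section 9.7 assumes a hazard ratio of 0.80 and asks for at least 80% probability of observing a ratio below 1. With 1:1 allocation, P(HR<1) = Φ(|ln HR| × √D / 2). For D = 57 this is Φ(0.2231 × 7.550 / 2) = Φ(0.842) = 0.800. Solving for 80% gives D = 56.9. The plan reproduces, with nothing to spare.

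**Inputs from the protocol.** 110 patients per arm, enalapril event rate 0.13 per patient-year (used as a hazard, the scale of Table 9-1), LCZ696 rate 0.8 × 0.13 = 0.104, accrual over 22 months, close at 40 months, mean follow-up 28.5 months (2.375 years, Section 3.1), visits every 4 months after month 6.

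**Assumptions.** The share r of an arm that stops visits, is followed remotely and never returns is not in the protocol, so a range is used. Stopping time is uniform over follow-up and unrelated to risk, and remote follow-up finds every event.

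**Hand calculation.** An event-free remote patient loses on average half the follow-up plus half a visit interval: 2.375/2 + 2/12 = 1.354 years.

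- Enalapril: event-free fraction exp(−0.13 × 2.375) = 0.734; time at risk per patient (1 − 0.734)/0.13 = 2.04 years; fraction of time lost = r × 0.734 × 1.354 / 2.04 = 0.487r.
- LCZ696: event-free fraction 0.781; time at risk 2.10 years; fraction lost 0.503r.

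The events are unchanged, so each arm's rate is its true rate divided by (1 − fraction lost). For 5% on enalapril and 10% on LCZ696:

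- Enalapril: 0.13/(1 − 0.0243) = 0.1332
- LCZ696: 0.104/(1 − 0.0503) = 0.1095
- Ratio: 0.1095/0.1332 = 0.82

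**Simulation.** 12,000 trials per scenario with the same inputs, plus an assumed non-CV death rate of 3% per year, fitting a Cox model under Section 9.4.3 with later events counted:

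| Remote share, enalapril / LCZ696 | HR by hand | HR simulated | P(HR<1) at 57 events |
|---|---|---|---|
| equal, 5% to 20% | 0.80 | 0.80 | 0.80 |
| 3% / 6% | 0.81 | 0.81 | 0.79 |
| 6% / 3% | 0.79 | 0.79 | 0.82 |
| 5% / 10% | 0.82 | 0.82 | 0.77 |
| 10% / 5% | 0.78 | 0.78 | 0.83 |
| 10% / 20% | 0.85 | 0.84 | 0.74 |
| 20% / 10% | 0.76 | 0.76 | 0.85 |

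With no true effect, a 5-point gap moves the chance of success from 0.50 to about 0.46 or 0.53.

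With balanced shares of 5, 10 and 20%, the enalapril rate rises from 0.130 to 0.133, 0.137 and 0.144 per year. The 30-month Kaplan-Meier incidence rises from 27.7% to 28.4, 29.0 and 30.4%.

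**Second parameterisation.** A separate large-sample calculation used annual stopping rates and no non-CV death. With 10% per year in both arms the ratio is 0.803; with 10% on enalapril and 5% on LCZ696 it is 0.761; reversed, 0.846. Over 2.375 years these rates mean that about 1 − exp(−0.2375) = 21% and 1 − exp(−0.119) = 11% stop, so they agree with the 20/10 and 10/20 rows.

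**Check of the remedy.** Censoring at the last contact with known event-free status returns 0.80 in every scenario. So does cutting both events and censoring at the last visit.

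**The case against.** **The asymmetry is inferred.** No sentence says that events after the last visit count while event-free time does not, and Section 9.4.4 speaks only of components. But Section 9.4.3 limits the censoring date of patients without events and places no limit on events. Section 3.1.1.3 collects events throughout the epoch, and the analysis is by randomised arm on the full analysis set. A confirmed event found remotely has no stated ground for exclusion.

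**A telephone contact might be a visit.** Section 3.1.1.3 speaks of visits in person, and calls follow the visit schedule. On that reading the problem disappears, and the analysis plan, not shown here, could say so. But Sections 5.5.9 and 6 make the telephone what happens when visits are not attended, and Section 9.4.3 does not depart from that.

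**The affected group may be small.** This stands as a limit on size. All patients are called back for Visit 299, and those who attend are censored correctly. Section 4 expects about 180 of 220 to complete, so about 40 do not, and deaths and consent withdrawals come out of the same 40. The 3-, 5- and 10-point gaps need about 10, 17 and 33 remote-only patients (110 × 0.09, 0.15 and 0.30), so the last is an extreme. The simulated 3% annual non-CV death rate is also high beside the statement in Section 3.2.1 that about 80% of deaths are CV, but the hand calculation uses no such deaths and gives the same ratios.

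**Blinding makes imbalance unlikely.** It makes a large imbalance less likely. It does not exclude one, because tolerability may differ between the drugs. No direction can be predicted. A 3-point gap changes the probability of success by only one or two points.

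**The reported event rate may be unaffected.** Section 9.4.2 describes it as adjusted for treatment exposure, so it may not use this follow-up time. The Kaplan-Meier curves do.

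**Conclusion.** The rule is wrong as written: for patients followed remotely, it makes the length of follow-up depend on the outcome. With balanced remote follow-up the hazard ratio is essentially unbiased, and only the absolute incidence is overstated, by 0.7 to 2.7 percentage points at 30 months for shares of 5 to 20%. With an imbalance of 3 to 5 points, the ratio moves by about 0.01 to 0.02 either way from 0.80, and P(HR<1) lies between 0.77 and 0.83. A 10-point gap would give 0.84 or 0.76 but would use up most of the expected non-completers.

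These sizes rest on assumed shares, stopping unrelated to risk and complete remote capture of events. The existence of the fault does not. It should be fixed because the primary objective turns on the point estimate alone and the design meets its 80% target exactly, so even a small adverse shift falls below it. Cutting non-CV deaths at the preceding visit follows from the same rule but is negligible: about 0.4% on the rate, with the ratio unchanged.

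**What to change.** In Section 9.4.3, replace the last-visit date with the last date on which the patient was known to be free of a primary event from any source: visit, telephone, designee or health-care provider. Censor at the earliest of that date, consent withdrawal, non-CV death and the end of the core part. State that adjudicated primary events up to the end of the core part count whether or not the patient still attends visits.

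A sensitivity analysis that cuts both events and censoring at the last visit is optional. It is also unbiased in the simulation but loses a few events.

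The cost is one or two sentences. Before the core part database lock, confirm that last-contact dates are held in the database, because Sections 5.5.11 and 6 place contact attempts in source documents.
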